### **Purpose of the Study and Background**

### Purpose of the Study

Poor diet and excess weight during adolescence predicts excess weight and diet-related cancers during adulthood, yet there is little research on the risk factors that contribute to weight gain among adolescents. The National Academy of Medicine identifies exposure to food advertisements (ads)as a major predictor of poor diet among children (<12 years of age) because studies have shown that children who are exposed to food ads consume more calories than children who are exposed to nonfood ads. The few food ad studies that have included adolescents (13-17 years of age) found associations between self-reported exposure to television (TV)food ads and poor diet, but we do not know which mechanisms explain this relationship. It is also well established that food companies promote their least healthy products to Black consumers more than White consumers and perceive Black youth as trendsetters. But it is not known whether seeing racially congruent ads (i.e., the person in the ad and the viewer are the same race) places Black adolescents at higher risk of poor diet relative to Whites. Finally, most food ad research is based on TV ads, but food companies are increasingly targeting adolescents on social media. The overall objective of our three studies is to identify the extent to which exposure to Facebook food ads increases the number of calories purchased and consumed by Black and White adolescents. Guided by strong preliminary data, we will test three aims: 1)To evaluate the extent to which exposure to racially congruent vs. incongruent Facebook food ads causes Black vs. White adolescents to purchase more calories for a snack;2)To determine the extent to which exposure to many vs. few "likes" on Facebook food ads causes Black and White adolescents to purchase more calories for a snack; and 3)To test the degree to which visual attention to unhealthy foods, racially congruent people, and/or "likes" in Facebook ads explains the relationship between ad exposure and calorie intake.

### Background

Clear diet-related disparities exist among adolescents in the United States, and poor diet is linked to colon, kidney, and liver cancers. Black adolescents have higher rates of overweight and obesity (38.2%) than White adolescents(26.3%)and face higher risks for diet-related cancers later in life.And the prevalence of obesity continues to increase among adolescents from low-income households, but not other income groups. Biologically, adolescents may make unhealthy food choices due to underdeveloped impulse control and greater neural sensitivity to reward in the nucleus accumbent compared to adults and children. Psychologically, adolescents are more likely than adults to focus on the present instead of long-term healthand a strong need to belong leads them to mimic cultural influences (e.g., social media, television [TV]).Further, the National Academy of Medicine identifies exposure to food advertisements (ads) as a major predictor of poor diet among children (<12 years of age), and eye-tracking studies show overweight children visually attend to food ads more than non-overweight peers.But far less is known about the influence of food ads on adolescents (age 13–17 years)., Some studies show adolescents' self-reported food ad exposure is linked with poor diet,but we do not know which mechanisms explain this relationship. It is also well established that food companies promote their least healthy products to Black consumers more

<sup>1 de Ferranti SD, Gauvreau K, Ludwig DS, Neufeld EJ, Newburger JW, Rifai N. Prevalence of the metabolic syndrome in American adolescents: findings from the Third National Health and Nutrition Examination Survey. *Circulation*. 2004;110(16):2494-2497.

<sup>2 Cook S, Weitzman M, Auinger P, Nguyen M, Dietz WH. Prevalence of a metabolic syndrome phenotype in adolescents: findings from the third National Health and Nutrition Examination Survey, 1988-1994. Arch Pediatr Adolesc Med. 2003;157(8):821-827.

<sup>3 Lobstein T, Baur L, Uauy R, IASO International Obesity TaskForce. Obesity in children and young people: a crisis in public health. *Obes Rev.* 2004;5 Suppl 1:4-104.

<sup>17 McClure AC, Tanski SE, Gilbert-Diamond D, et al. Receptivity to television fast-food restaurant marketing and obesity among U.S. youth. *Am J Prev Med.* 2013;45(5):560-568. PMCID: PMC3934414.

<sup>18 Story M, Neumark-Sztainer D, French S. Individual and environmental influences on adolescent eating behaviors. *J Am Diet Assoc*. 2002;102(3 Suppl):S40-S51.

than White consumers,,,,,,and perceive Black youth as trendsetters.But it is not known whether seeing racially congruent ads(i.e., the person in the ad and the viewer are the same race) places Black adolescents at higher risk of poor diet relative to White adolescents. Finally, most food ad research is based on TV ads, but social media is a new advertising frontier that may pose serious health risks. Adolescents' daily social media use (2.0 hours) now rivals time spent watching TV (2.6 hours),32>90% of them use social media,and they command \$175billion in spending power.And global expenditures for social media ads have now surpassed \$35billion annually.

# **Study Design**

The overall objective is to determine the extent to which racially congruent Facebook food ads influence adolescents' food purchases and actual caloric intake. We will accomplish these objectives by conducting three randomized controlled trials (RCTs). The first two aims trials will involve 15minute online surveys in which participants (Black and White adolescents) will rate ads then complete a "food purchasing" task through a virtual vending machine. The third trial will involve an in-person, hour long lab study where participants will be shown ads while investigators covertly monitor their eye movements. The first RCT will answer the research question "Does exposure to racially congruent vs. incongruent Facebook ads for unhealthy foods cause Black (vs. White) adolescents to purchase snacks with more calories?". The second RCT will answer: "Does exposure to many "likes" (vs. few "likes") on Facebook ads for unhealthy foods lead to even higher calorie purchases for both Black and White adolescents?". Lastly, the hour-long study will answer the question: "To what extent does the visual attention to foods vs. people vs. "likes" in ads predict adolescents' caloric intake?" (Aim 3). For the first two online survey trials, we will measure the average calories purchased for a snack and for the last trial we will measure the average calories consumed.

<sup>19 Harris JL, Schwartz MB, LoDolce M, et al. Sugary drink FACTS 2014: Some progress but much room for improvement in marketing to youth. *Rudd Center for Food Policy and Obesity: New Haven, CT*. 2014.

<sup>20 Harris JL, Schwartz MB, Munsell CR, et al. Fast food FACTS 2013: Measuring progress in nutrition and marketing to children and teens. *Yale Rudd Center for Food Policy and Obesity*. 2013.

<sup>21 Grier SA, Kumanyika S. Targeted marketing and public health. Annu Rev Public Health. 2010;31:349-369.

<sup>22 Harris JL, Shehan C, Gross R, et al. *Food Advertising Targeted to Hispanic and Black Youth: Contributing to Health Disparities*. Rudd Center for Food Policy & Obesity; 2015.

<sup>23 Story M, French S. Food Advertising and Marketing Directed at Children and Adolescents in the US. *Int J Behav Nutr Phys Act*. 2004;1(1):3.

## **Characteristics of the Research Population**

### Number of Subjects

For this study we intend to recruit a total of 3,032 adolescents (1,252 in Aim 1; 1,300 in Aim 2; and 480 in Aim 3—the in-person lab study). Participants will be selected through Dynata, a survey firm. A power analysis was conducted to determine the sample size in which the size of 1,252 participants provides 80% power to detect an effect size of 0.2 SD between conditions.

### Gender of Subjects

We will recruit males and females because research shows pre-adolescent males consume more fast food than females. We will therefore examine differences in responses based on sex. Adjustment of primary analysis will be undertaken to accommodate any imbalances.

#### Age of Subjects

We intend to recruit a total sample of 3,032 adolescents ages 13-17 years. This age group is chosen as a follow up to the online within-subject pilot experiment and because of the purpose of the study being to gain more knowledge specifically on how targeted ads affect this age group.

### Racial and Ethnic Origin

We will recruit 3,032 adolescents that identify as only non-Latino White or only Black/African American. The purpose being that targeted ads usually appeal to Black youth in particular. This marketing tactic is a potent one worth further investigation since most of the targeted ads are for unhealthy foods. And black adolescents experience higher rates of obesity and report higher social media use than their peers. We will use the White participants as a comparison group since they are featured in most ads and are, therefore, unlikely to experience heightened effects from racially targeted ads. There are plans to study other racial/ethnic groups in future research, but we would not be adequately powered in this proposal to understand the effects for each racial/ethnic group.

#### **Inclusion Criteria**

Participants must: 1) be 13–17 years of age; 2) identify as only non-Latino White or only Black/African American; 3) report that they log into Facebook at least once daily; and 4) read and speak English. We will include the SCOFF, screening tool—a five-item, validated eating disorders assessment—at the end of the study. We will not exclude adolescents who report symptoms. If a participant reports having symptoms, we will provide them resources as described in our Human Subjects attachments.

<sup>29 Hill LS, Reid F, Morgan JF, Lacey JH. SCOFF, the development of an eating disorder screening questionnaire. *Int J Eat Disord*. 2010;43(4):344-351.

### **Exclusion Criteria**

Any criteria not met as listed above will bar an adolescent from participating in the study.

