**Aim 3:** Participants will visit our collaborator [name] in her lab —located at NYU Washington Square Campus—and sit in front of a Tobii eye-tracking computer. The computer monitor displays an advertisement and youth view it as they would any other type of document on a computer. Eye-tracking technology allows for the documentation of fixations, an objective measure of attention, which occurs when an individual pauses to examine or interpret a component of an advertisement or image. The Tobii eye tracking device allows moderately free head movements. It returns a real-time estimate of the left and right eye gaze positions on the screen, as well as the 3D position of the two eyes with respect to the screen center. After obtaining consent and assent in-person, we will ask

participants to "answer a few questions about how they are feeling today" and hunger will be one of the items they rate, which will allow us to unobtrusively measure baseline hunger and control for it during analyses. We will then tell them that we will show them a series of images that are for their viewing pleasure, and that we have snacks and a drink they can enjoy as a thank you for participating. Participants will view 30 ads per block that appear at a predetermined rate to hold total viewing time constant across all ads. Researchers will calibrate the eye-tracking computer using a guise developed by our collaborator [name] that asks the participant to count the number of times a ball bounces on the screen (n = 6), "so you can take a moment to let your mind rest after rushing through the busy city to arrive at the lab today." [name] has used this technique on >1,000 participants and <1% noted suspicion.

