During the eye-tracking task, snacks will be positioned in bowls on a Cardinal Detecto stainless steel scale that looks like a serving tray but transmits weight information wirelessly to the control room. Similar to previous food ad studies,we will include two unhealthy snacks and two healthy snacks with a 20-ounce bottle of water. The unhealthy snacks will include M&Mcandies (high-fat, sweet) and Doritos chips (high-fat, savory). The healthy snacks will include Quaker Rice Cakes (lowfat, savory) and grapes (low-fat, sweet). To minimize the risk of ceiling effects (i.e., where participants eat all the food), we will include 150g of each snack: M&Ms (296-ml bowl), Doritos and Quaker Rice Cakes (1,419-ml bowls), and grapes (473-ml bowl). Our pilot data also suggest—and a systematic review reinforces—that most participants eat during food ad studies. To conclude the study, participants will complete demographic questions (Table 1). We will use a funneled debriefing procedure to ask participants what they believed was the purpose of the study so we can test for moderation of effects as a function of awareness during analyses. We will disclose the purpose of the study, solicit questions, conduct a second assent procedure after disclosing eye-tracking was used and was ethically approved, and provide the same information from the debriefing form in Aim 1 and 2 (section E.3.4). Finally, we will distribute \$35 compensation in cash and subway/bus fare to cover travel costs. Those who travel by other means will also receive the travel fare.

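### Aim 3 serves snacks to 13–17 year olds under the eligibility list shared with the online surveys: no food-allergy check is described, and the risk section says no snacks are provided

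*Combined protocol and SAP*

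**What the plan says.** The Number of Subjects section plans "1,252 in Aim 1; 1,300 in Aim 2; and 480 in Aim 3—the in-person lab study". All of them fall under one Inclusion Criteria list: an age range, a race criterion, and then "3) report that they log into Facebook at least once daily; and 4) read and speak English". The Exclusion Criteria section consists of one sentence: "Any criteria not met as listed above will bar an adolescent from participating in the study". Eating-disorder symptoms are screened at the end of the study and do not exclude: "We will not exclude adolescents who report symptoms".

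In Methods & Procedure, Aim 3, participants are told that "we have snacks and a drink they can enjoy as a thank you for participating". Four foods are set out in bowls, 150 g of each. On the unhealthy side: "The unhealthy snacks will include M&Mcandies (high-fat, sweet) and Doritos chips (high-fat, savory"). On the healthy side: "The healthy snacks will include Quaker Rice Cakes (lowfat, savory) and grapes (low-fat, sweet"). The Study Design section makes average calories consumed the measure for this trial.

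The Risk/Benefit Assessment notes that researchers in laboratory studies of food ads supply snacks, and then says that this study does not. The Aim 3 consent section says that the caregiver's form explains the risks and the measures against them, and that staff discuss these with the adolescent before assent. The Aim 3 analysis plan removes participants only for a low eye-tracking sampling rate.

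**The concern.** The four criteria are adequate for Aims 1 and 2, where no food changes hands. In Aim 3 the participants are minors and the exposure includes food. An adolescent who is allergic to one of the four snacks meets every listed criterion. The questions asked before the session concern how the participant feels, including hunger; no item on allergy or diet is described. The caregiver is the person most likely to know of an allergy and is already being asked to sign a form, but no step collects that information. The protocol therefore relies on a 13–17 year old to raise the matter unprompted. Because the risk section overlooks the served food, a reader of that section would not see that the exposure exists.

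There is a lesser analytic issue. Intake that is limited by allergy or diet varies less with ad type or visual attention, which weakens the attention–intake relation that Aim 3 is sized to detect. As described, the data could not separate an adolescent who cannot eat a snack from one who chose not to.

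**Working it through.** **Text check.** These are the places where an allergy check could appear in the protocol.

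| Section | What it covers | Allergy or diet check? |
|---|---|---|
| Inclusion Criteria | Age, race, Facebook use, English | No |
| Exclusion Criteria | Failing one of those four | No |
| Methods & Procedure, Aim 3 | Feelings and hunger at baseline; snacks in bowls | No |
| Consent/Assent, Aim 3 | Risks explained to caregiver and adolescent | No information collected |
| Data Analysis, Aim 3 | Removal for low sampling rate | No rule for non-eaters |
| Risk/Benefit Assessment | States that no snacks are provided | Contradicts the Aim 3 procedure |

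**Reproducing the plan's figure.** Data Analysis, Aim 3, gives 200 per race for 80% power at a correlation of 0.2. No alpha is stated for Aim 3, so two-sided 0.05 is assumed. With Fisher's z:

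n = ((1.960 + 0.842) / atanh(0.2))² + 3 = (2.802 / 0.2027)² + 3 ≈ 194.

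At n = 200, power = Φ(√197 × 0.2027 − 1.960) = Φ(0.886) = 81.2%. The plan's figure reproduces.

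**Inputs for the dilution.** The documents give no prevalence f of restriction, so 2%, 5% and 10% are assumed: about 10, 24 and 48 of 480. They give no intake mean or SD for Aim 3 either. The Aim 1 planning values are borrowed: 400–600 calories with SD 400, so k = mean/SD runs from 1.0 to 1.5, with 1.25 at the midpoint. Suppose that affected adolescents eat a fraction c of what they would otherwise eat. With m = 1 − f + fc and s = 1 − f + fc², the correlation becomes

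r′ = 0.2 × m / √(s(1 + k²) − k²m²).

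For c = 0 (none of the four snacks eaten) this reduces to 0.2 × √(1 − f) / √(1 + fk²).

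Worked case, k = 1.25, f = 10%:
- c = 0: r′ = 0.2 × √0.90 / √1.156 = 0.176.
- c = 0.5: m = 0.95 and s = 0.925, so r′ = 0.2 × 0.95 / √(0.925 × 2.5625 − 1.5625 × 0.9025) = 0.19 / √0.960 = 0.194.

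Power at 200 per race, k = 1.25 (unrestricted: 81.2%):

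| Intake of affected adolescents | f = 2% | f = 5% | f = 10% |
|---|---|---|---|
| 75% of usual (roughly one snack lost) | 81.1% | 80.9% | 80.6% |
| 50% of usual | 80.7% | 80.0% | 78.7% |
| None of the four snacks | 79.2% | 76.0% | 70.6% |

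Partial restriction costs 0.1 to 2.5 points. Total abstention by 10% costs 10.6 points. Over k = 1.0 to 1.5, the half-intake row at 10% runs from 79.3% to 78.1%, and the abstention row at 10% from 72.8% to 68.1%.

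**Using the planned recruitment.** The plan recruits 480, or 240 per race if split equally (an assumption). Allowing the 5% eye-tracking loss that the plan treats as an upper figure, 480 × 0.95 / 2 = 228 per race. Power at k = 1.25 is then 86.0% with no restriction, and 84.2%, 81.3% and 76.3% if 2%, 5% and 10% eat none of the snacks.

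**The case against.** The strongest objection is that the relevant documents are not all in view. The consent forms were removed before review, and the Inclusion Criteria section refers to Human Subjects attachments. Either could carry an allergy notice. Eating is optional, the snacks are offered openly, the deception concerns the study's purpose and the eye-tracking, and two researchers supervise each session. All of this stands and lowers the risk. It does not explain why the eligibility and procedure sections are silent, or why the risk section denies that snacks are given.

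A reader might go further in four ways that the documents do not support.

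- That an allergic adolescent has to be enrolled. The criteria are conditions for entry; nothing bars such an adolescent, but nothing compels enrolment.
- That restricted participants cannot respond to the ads. This is true only of someone who eats none of the four snacks. Avoiding one or two narrows the range of intake.
- That power falls to about 71%. This needs 10% total abstention and only 200 per race. The documents support neither the prevalence nor the abstention, and 480 are to be recruited. If the planning correlation of 0.2 already reflects an unscreened population, part of the dilution would be counted twice.
- That the Black–White comparison is biased. No section suggests that restrictions differ by race. In the ad-type model, the participant random intercept absorbs a stable difference in level, which leaves dilution rather than bias.

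Excluding every adolescent with a dietary restriction would also sit badly with a protocol that is otherwise deliberately inclusive.

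**Conclusion.** The point holds as a safety and consistency gap in Aim 3. The protocol describes no food-allergy check before minors are offered four named snacks, and its risk section contradicts its procedure on whether snacks are provided. This rests on the text alone and needs no assumption about prevalence. It is limited to the sections available for review.

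The statistical consequence is secondary and probably small. At the midpoint k of 1.25, the loss at 200 per race is nil to about 2.5 points for partial restrictions at 2–10% prevalence, and up to about 10 points only if 10% eat none of the snacks. These figures assume two-sided alpha 0.05 and an intake mean and SD borrowed from the Aim 1 purchase planning. The sample size of 200 per race is not shown to be wrong.

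**What to change.** Reconcile the Inclusion and Exclusion Criteria, the Aim 3 procedure, the Risk/Benefit Assessment and the Aim 3 consent section:

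- Add an Aim 3 question to the caregiver at consent on food allergy or intolerance to the snacks offered. Place it within a general health and diet list so that the cover story is kept. The investigators should set, and the protocol should state, how a positive answer is handled.
- Correct the risk section so that it says that Aim 3 serves food, and make the description of risks in the Aim 3 consent section agree.
- Record other dietary restrictions with the same question. Do not exclude on them. Prespecify a sensitivity analysis of intake that adjusts for restriction status or leaves out restricted participants.

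The cost is one more caregiver question, one recorded variable and possibly a few adolescents lost. No extra visit is needed.

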#### **Vulnerable Subjects**

In this study we will include 13–17 year olds because they are the target population and highly susceptible to targeted food ads.

# **Methods & Procedure**

**Aim 1:** After obtaining parental permission and assents, participants will view and rate 18 ads in the online survey. They will view and rate one ad before viewing and rating the next ad. They will then complete the food purchasing task. In this task, six foods and six beverages from the brands that target adolescents the most will appear in a virtual vending machine embedded in the online survey. Half of the food items will be healthy snacks and half will be unhealthy, as scored by the Nutrient Profile Model, a validated nutrition rating tool designed by nutritionists and used in public health studies. Three of the beverages will be sugar-sweetened beverages and three will be the zero-calorie versions of those sugar-sweetened beverages. Participants will select one food item and one beverage they would like to consume. To incentivize actual purchasing behavior, we will tell them we will provide \$8 for their snack purchases and they can keep any money they choose not to spend. We will also tell them that we will mail the items to their home. This approach will incentivize adolescents to consider the trade-offs of keeping money vs. spending it on snacks, which is more representative of real-world purchasing behavior. In reality, we will provide the \$8 at the end of the study instead of mailing the items. After the food purchasing task, participants will complete demographic questions and then receive \$25 for participating and \$8 for their snack purchases

**Aim 2:** Parental consent and adolescent assent process will be obtained as described for Aim 1. After providing assent, participants will be randomized to view and rate 18 racially congruent Facebook food ads that feature many (>10,000) or few (<100) "likes." After viewing each ad, they will complete the ad rating questions for that ad (Table 2) before proceeding to the next ad. Participants will then complete the same food purchasing task described in Aim 1(section E.3.4.). Finally, they will complete the demographic questions. At the end of the study, they will view a debriefing statement similar to the statement from Aim 1 (sectionE.3.4). Dynata will then provide each participant with \$25 compensation and \$8 for the purchased snack products.

**Aim 3:** Participants will visit our collaborator [name] in her lab —located at NYU Washington Square Campus—and sit in front of a Tobii eye-tracking computer. The computer monitor displays an advertisement and youth view it as they would any other type of document on a computer. Eye-tracking technology allows for the documentation of fixations, an objective measure of attention, which occurs when an individual pauses to examine or interpret a component of an advertisement or image. The Tobii eye tracking device allows moderately free head movements. It returns a real-time estimate of the left and right eye gaze positions on the screen, as well as the 3D position of the two eyes with respect to the screen center. After obtaining consent and assent in-person, we will ask

participants to "answer a few questions about how they are feeling today" and hunger will be one of the items they rate, which will allow us to unobtrusively measure baseline hunger and control for it during analyses. We will then tell them that we will show them a series of images that are for their viewing pleasure, and that we have snacks and a drink they can enjoy as a thank you for participating. Participants will view 30 ads per block that appear at a predetermined rate to hold total viewing time constant across all ads. Researchers will calibrate the eye-tracking computer using a guise developed by our collaborator [name] that asks the participant to count the number of times a ball bounces on the screen (n = 6), "so you can take a moment to let your mind rest after rushing through the busy city to arrive at the lab today." [name] has used this technique on >1,000 participants and <1% noted suspicion.

During the eye-tracking task, snacks will be positioned in bowls on a Cardinal Detecto stainless steel scale that looks like a serving tray but transmits weight information wirelessly to the control room. Similar to previous food ad studies,we will include two unhealthy snacks and two healthy snacks with a 20-ounce bottle of water. The unhealthy snacks will include M&Mcandies (high-fat, sweet) and Doritos chips (high-fat, savory). The healthy snacks will include Quaker Rice Cakes (lowfat, savory) and grapes (low-fat, sweet). To minimize the risk of ceiling effects (i.e., where participants eat all the food), we will include 150g of each snack: M&Ms (296-ml bowl), Doritos and Quaker Rice Cakes (1,419-ml bowls), and grapes (473-ml bowl). Our pilot data also suggest—and a systematic review reinforces—that most participants eat during food ad studies. To conclude the study, participants will complete demographic questions (Table 1). We will use a funneled debriefing procedure to ask participants what they believed was the purpose of the study so we can test for moderation of effects as a function of awareness during analyses. We will disclose the purpose of the study, solicit questions, conduct a second assent procedure after disclosing eye-tracking was used and was ethically approved, and provide the same information from the debriefing form in Aim 1 and 2 (section E.3.4). Finally, we will distribute \$35 compensation in cash and subway/bus fare to cover travel costs. Those who travel by other means will also receive the travel fare.

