### **Data Analysis**

**Aim 1-** Statistical considerations: Power and sample size: We wish to have adequate power to detect a difference of ~20% in calories purchased between the groups. Data from studies on adolescents' snack choices indicated an average of 400–600 calories. Thus, we wish to detect a between-group difference of ~100 calories. Estimates of standard deviation of food choices vary widely. Most estimates are 100–300 calories, but to be conservative, and because we do not have direct data on purchases in an online survey, we assume a standard deviation of 400calories. Accounting for participants who fail the attention check item, and using a two-sided Type I error rate of 0.017to control the experiment-wise error rate to 0.05, a final sample size of 1,252 participants (100 pre-test participants that will not be part of the final sample, plus 288 per group in each of the four conditions =

<sup>30 Harris JL, Bargh JA, Brownell KD. Priming effects of television food advertising on eating behavior. *Health Psychol.* 2009;28(4):404-413.

<sup>31 Dias M, Agante L. Can advergames boost children's healthier eating habits? A comparison between healthy and non-healthy food. *J Consumer Behav*. 2011;10(3):152-160.

<sup>32 Harris JL, Speers SE, Schwartz MB, Brownell KD. US Food Company Branded Advergames on the Internet: Children's exposure and effects on snack consumption. *Journal of Children and Media*. 2012;6(1):51-68.

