1,252 total participants)provides 80% power to detect a difference of 80 calories between the groups who see racially congruent vs. racially incongruent ads. This sample size also provides 80% power to detect a difference of 113 calories between White adolescents who see racially congruent ads and Black adolescents who see racially congruent ads. Secondary outcomes: This sample size provides 80% power to detect an effect size of 0.2 standard deviation (SD)between outcomes. Analytic plans: Descriptive analyses: All data will be summarized prior to analysis, using means, medians, ranges, and standard deviations for continuous variables and frequencies for categorical variables. BMI-z scores, which a readjusted for age and sex, will be calculated using Centers for Disease Control growth charts. Participants who fail our data integrity check questions will be excluded. This is expected to be ~9% of participants based on our pilot studies and previous work with adolescents.We will assess balance by randomization status with respect to demographic and behavioral factors. Adjustment of primary analyses will be undertaken to accommodate any imbalances

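### Aims 1 and 2 describe no hunger rating before the ads, although Aim 3 does, so they give up some precision and cannot adjust the Black vs White contrasts for hunger

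*Combined protocol and SAP*

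**What the plan says.** Methods & Procedure, Aim 3, has participants answer a short set of questions about their current state after consent and assent and before any ad. Hunger is one item, "which will allow us to unobtrusively measure baseline hunger and control for it during analyses". The Aim 3 model in Data Analysis lists ad type and random effects for participant and block order. It does not list hunger.

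For Aim 1 the same section says: "After obtaining parental permission and assents, participants will view and rate 18 ads in the online survey". The purchasing task follows, then the demographic questions. For Aim 2: "After providing assent, participants will be randomized to view and rate 18 racially congruent Facebook food ads". Ratings are completed after each ad, then come the same purchasing task and the demographic questions. Neither description contains a hunger item or any question block before the first ad, and no reason is given for the difference from Aim 3.

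Calories purchased is the primary outcome in both aims. The covariates named in Data Analysis are eating restraint and eating-disorder symptoms (Aim 1), and demographic and behavioural characteristics that are not itemised, with eating-disorder symptoms as a sensitivity analysis (Aim 2). The eating-disorder screen is given at the end of the study.

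**The concern.** Current hunger is a plausible predictor of how many calories a person picks for a snack, and online participants may answer at any time of day. Aim 3 provides for it; Aims 1 and 2, which hold most of the sample, do not. The gap cannot be closed later, because a hunger rating taken after 18 food ads could differ by condition.

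Two things are at stake. One is precision in the primary regressions. The other is the Black vs White comparison among participants who see the same kind of ad. The plan powers this comparison in both aims, but race is not randomised. If the groups differ in hunger when they respond, the contrast mixes that difference with the response to the ads, and without a measurement it cannot be adjusted for. The same gap keeps hunger out of the planned balance checks.

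**Working it through.** **Inputs from Data Analysis.**
- Test level: "using a two-sided Type I error rate of 0.017to control the experiment-wise error rate to 0.05"; Aim 2 uses the same level.
- Spread: "we assume a standard deviation of 400calories"; Aim 2 assumes the same.
- Aim 1 allocation: "plus 288 per group in each of the four conditions", so 2 × 288 = 576 per ad condition. Aim 2: 600 per condition, taken here as 300 per race within condition.
- Loss to integrity checks: about 9% in Aim 1 and under 9% in Aim 2; 9% is used for both.
- Stated results, Aim 1: "provides 80% power to detect a difference of 80 calories between the groups who see racially congruent vs. racially incongruent ads" and "80% power to detect a difference of 113 calories between White adolescents who see racially congruent ads and Black adolescents". Aim 2: 78 and 110 calories.

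**Step 1: reproduce the plan's figures with no covariate.** The detectable difference is (z for two-sided 0.017 + z for 80% power) × SD × √(2/n) = (2.387 + 0.842) × 400 × √(2/n), with n per group after 9% loss.

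| Contrast | n per group | Computed (calories) | Stated (calories) |
|---|---|---|---|
| Aim 1, congruent vs incongruent | 576 × 0.91 ≈ 524 | 79.8 | 80 |
| Aim 1, Black vs White | 288 × 0.91 ≈ 262 | 112.8 | 113 |
| Aim 2, many vs few likes | 600 × 0.91 = 546 | 78.2 | 78 |
| Aim 2, Black vs White | 300 × 0.91 = 273 | 110.5 | 110 |

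The stated figures reproduce with the 9% loss included and no baseline covariate. They do not depend on hunger.

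**Step 2: effect of adding baseline hunger.** If hunger correlates r with calories purchased, beyond any other covariates in the model, the residual SD is 400 × √(1 − r²). The standard error and the detectable difference shrink by the factor √(1 − r²). The documents give no r, so the range is assumed.

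| Assumed r | √(1 − r²) | SE reduction | Aim 1: 80 becomes | Aim 2: 78 becomes | Equivalent extra sample, 1/(1 − r²) − 1 |
|---|---|---|---|---|---|
| 0.1 | 0.995 | 0.5% | 79.6 | 77.6 | 1.0% |
| 0.2 | 0.980 | 2% | 78.4 | 76.4 | 4.2% |
| 0.3 | 0.954 | 5% | 76.3 | 74.4 | 9.9% |
| 0.4 | 0.917 | 8% | 73.3 | 71.5 | 19.0% |

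**Step 3: the Black vs White contrasts.** An unadjusted contrast would be shifted by roughly the calorie-on-hunger slope times the difference in mean hunger between the groups. The documents give neither quantity, so no size is claimed.

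**Step 4: could an item outside the supplied text fill the gap?** Tables 1 and 2 are cited but not supplied. In the described order, the Table 2 ratings follow each ad. Table 1 is cited for the demographic questions, which in Aims 1 and 2 come after the purchase. An item in either would not be a pre-exposure baseline.

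**The case against.** The case for leaving Aims 1 and 2 as they are is substantial.

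- The outcomes differ. Aim 3 measures immediate eating from bowls. In Aims 1 and 2 participants choose one food and one drink, are told the items will be mailed, and weigh the purchase against keeping part of $8. Hunger may matter less there. This stands, and it is a reason to expect the lower end of the range.
- The sample is already ample for the stated target. By the same approximation, power at about 100 calories is already about 95% in Aim 1 (100/24.71 − 2.387 = 1.66) and 96% in Aim 2 (100/24.21 − 2.387 = 1.74) for the main contrasts. The SD of 400 is also set above most of the estimates cited. This stands: the precision gain is welcome but not needed for that target.
- The procedure text is condensed and leaves out things found elsewhere, such as the attention check, so silence is not proof of absence. This stands in part. The order it does describe has no block before the ads.
- A hunger question may hint at the food focus, which is hidden until the end in Aims 1 and 2, and cueing that is equal across arms can still change the size of an ad effect. Aim 3 is not a full precedent, because its participants are told of snacks beforehand. This is a genuine cost, though small beside 18 food ads.

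A reader might infer that the plan regards hunger adjustment as necessary, or singles hunger out. It does not: Aim 3 says only that the item makes control possible, and Aim 1 names other covariates. Nor do the documents support saying that Aim 3 already adjusts for hunger. The intent is in the procedures, but the model does not carry it.

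**Conclusion.** The inconsistency between the aims is real and unexplained, and correcting it is a cheap improvement rather than the repair of a flaw in validity. A reader might go further and infer that the primary comparisons are biased or that the power statements fail. Neither follows. Ad condition is randomised in both trials, so unmeasured hunger does not bias congruent vs incongruent or many vs few likes, and the stated detectable differences reproduce without it.

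The loss is a standard error larger by an amount that depends wholly on the assumed r (Step 2), plus the inability to adjust the two non-randomised race contrasts for hunger. The second is the stronger reason to act, although its size cannot be derived from the documents.

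**What to change.** Before data collection:

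1. Insert Aim 3's disguised question block, with hunger as one item, between assent and the first ad in Aims 1 and 2.
2. Pre-specify baseline hunger as a covariate in the linear regressions of calories purchased in both aims, including the models with participant race and its interaction with condition.
3. Name hunger in the Aim 3 model in Data Analysis so that it matches the procedures.

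If the team prefers not to add the item, a sentence giving the reason would resolve the inconsistency.

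The cost is a few extra items in a 15-minute survey and one model term. The downside is slight food cueing, equal across arms, in a study whose food focus is not disclosed until the end; placing hunger among unrelated items limits it. The sample size need not change.
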